### **2.3.6 Stratification**

Randomization will be stratified on:

- Region
  - North America: Canada and USA
  - Europe: Bulgaria, Czech Republic, Hungary, Poland and Russia
  - Asia: Australia, and Taiwan
- MRI/CRP classification

Subjects will be classified as MRI+/- depending on whether or not they have evidence of sacroiliitis on MRI at Screening based on the ASAS/OMERACT definition. Subjects will be classified as CRP+/- based on the CRP value obtained at the second Screening visit scheduled to occur 3 to 5 days prior to Baseline. Subjects will be categorized as CRP+ if their CRP value is above the level indicative of inflammatory disease at this visit. Otherwise, they will be considered CRP-. Based on these definitions, the stratification for MRI/CRP classification will have the following 3 levels:

- MRI+/CRP+
- MRI+/CRP-
- MRI-/CRP+

Subjects who are MRI-/CRP- are not eligible for randomization. The interactive response system (IXRS) will be designed to ensure that at least 20% of the randomized subjects belong to one of the three clinical subgroups above.

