#### **4.4 Multicenter studies**

Due to the low number of subjects expected to be recruited per site, results will not be tabulated by individual sites. However important protocol deviations will be tabulated by region and the number of subjects randomized per region will also be presented. Listings will show the region and site for each subject. In addition, as subject randomization is stratified by region, efficacy analyses models will include region as a factor as described in [Section 8](#).

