### 8.3 Analysis of other efficacy variables during the double-blind 52-week treatment period

The efficacy analyses described in this section are not part of the multiplicity-controlled testing procedure described in [Section 8](#). The p-values reported for these analyses will not be adjusted for multiplicity and will be considered nominal. Derivations for these other efficacy variables can be found in [Section 8.3.1](#).

Continuous other efficacy variables will be analyzed using an ANCOVA model including Baseline score as a covariate, and fixed effects for treatment group, region, and MRI/CRP classification. The treatment differences and corresponding 95% CIs will be calculated based upon the adjusted least squares means. Missing values or values observed after discontinuing the double-blind study treatment will be imputed using LOCF. In addition, as described in [Section 4.2.3](#), an observed case analysis will also be performed for subjects still on the original double-blind study treatment. Tables for continuous variables will display descriptive statistics for Baseline, absolute values and change from Baseline at post-Baseline time points.

Categorical other efficacy variables will be analyzed using a logistic regression model with factors of treatment group, region, and MRI/CRP classification (MRI+/CRP+; MRI+/CRP-; MRI-/CRP+). If the logistic regression model is unable to converge, then the MRI/CRP classification variable may be dropped from the model to facilitate convergence. Tables for the binary variables will display the responder rates for the various time points. Analyses will be presented in 2 ways (as described in [Section 4.2.3](#)). First, they will be presented where the denominator is all subjects in the FAS for the given treatment group. This is essentially a NRI approach as subjects who have not achieved the given outcome (whether observed or not) or subjects who discontinue double-blind study treatment are considered as not having responded. Second, the responder rates will be presented for the FAS using Observed Case data. Subjects still on the original double-blind study treatment and with response will be analyzed, with the denominator based on the number of observed values at the given time point.

Continuous other efficacy variables to be analyzed using change from Baseline are:

- BASDAI and BASFI at Weeks 1, 2, 4, 8, 16, 20, 24, 28, 32, 36, 40, 44, 48
- ASDAS at Weeks 2, 4, 8, 12, 16, 20, 24, 28, 32, 36, 40, 44, 48, and 52

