- SI joint SPARCC score <2 at Weeks 12 and 52
- Uveitis flares, IBD exacerbations and Psoriasis exacerbations at Baseline and Weeks 4, 12, 24, 36, 48 and 52 (Summary statistics provided only)
- EQ-5D 5-Item health status at Weeks 4, 12, 24, 36, 48, and 52

For the ‘resource utilization’ variables ‘number of concomitant medical procedures’, ‘number of health care provider consultations not foreseen by the protocol’, ‘number of hospitalizations’, and ‘number of emergency room visits’ descriptive statistics and frequency distributions will be presented for the entire double-blind period.

For the WPS scores, Question 1 responses will be summarized descriptively. Question 2-9 will be summarized by descriptive statistics as well. Treatment comparisons for Question 2 through Question 9 will be performed using a mixed-effect repeated-measures model (MMRM). For each individual question, a separate MMRM will be fitted for the change from baseline, including fixed effects of baseline, treatment, visit, treatment-by-visit interaction and baseline-by-visit interaction, including a random effect of subject and using an unstructured variance-covariance structure. The Kenward-Rogers method will be applied to estimate the denominator degrees of freedom. If convergence problems arise, the covariance structure will be assumed to be autoregressive first order (AR[1]). If that still leads to numerical problems, the more general case, the Toeplitz (TOEP) covariance structure will be used. If all methods above fail to produce a solution, the covariance structure Compound Symmetry (CS) will be used. The least-square means of the treatment difference by visit including 95% confidence intervals and p-values for the test on treatment differences will be summarized.

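### The WPS mixed model omits the randomization strata, pairs a random subject effect with an unstructured covariance, and falls back to AR(1) before the more general Toeplitz structure

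*SAP*

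**What the plan says.** **WPS model.** SAP Section 8.3 fits a separate model of change from baseline for each of WPS Questions 2 to 9, "including fixed effects of baseline, treatment, visit, treatment-by-visit interaction and baseline-by-visit interaction", and then "including a random effect of subject and using an unstructured variance-covariance structure". Denominator degrees of freedom follow Kenward-Roger. Differences by visit are reported with 95% confidence intervals and p-values.

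**Fallback.** If the unstructured model does not converge, AR(1) is assumed. If that also fails, "the more general case, the Toeplitz (TOEP) covariance structure will be used". If everything before it fails, "the covariance structure Compound Symmetry (CS) will be used".

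**Strata.** Section 2.3.6 states "Randomization will be stratified on" region and MRI/CRP classification, each with three levels. Section 4.4 gives stratification by region as the reason why "efficacy analyses models will include region as a factor", and refers to Section 8 for the description. In Section 8.3 the ANCOVA for the other continuous variables has "fixed effects for treatment group, region, and MRI/CRP classification". The logistic model for categorical variables in that section carries the same two factors.

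**Status.** Section 2.2.1.3 lists WPS among the other efficacy variables. Section 8.3 places these analyses outside the multiplicity procedure, with nominal p-values.

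**The concern.** Three features of one paragraph sit badly together.

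1. **Strata.** The model leaves out both factors used to stratify randomization. Stratification removes between-stratum variation from the treatment contrast, but a model without the strata keeps that variation in its residual variance. The reported standard errors then do not match the design, and WPS is handled differently from its neighbours without a stated reason.

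2. **Redundant subject effect.** An unstructured within-subject covariance already contains whatever a random subject intercept could add. Specifying both gives the software one parameter too many. That can produce a zero or arbitrary subject variance, a Hessian warning or non-convergence, none of which says anything about the data.

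3. **Fallback order.** Such a warning would send the analysis to AR(1), a two-parameter structure, ahead of Toeplitz, which the plan itself describes as more general. Kenward-Roger inference is model-based, so the intervals and p-values depend on the covariance structure being adequate.

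At stake are the precision and the model-based standard errors of eight sets of by-visit WPS comparisons. Nothing in the primary or hierarchical secondary analyses depends on them.

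**Working it through.** The plan states no figure on this point, so there is none to reproduce. The checks are on model structure, plus one assumed range.

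**Inputs**
- Fixed effects, covariance terms and fallback order: Section 8.3.
- Strata, region (3 levels) and MRI/CRP classification (3 levels): Section 2.3.6.
- Number of WPS visits *k*: not given in the text on WPS, so *k* = 3 to 12 was taken as an assumed range.
- *R*², the share of variance left after baseline and baseline-by-visit that the strata explain: not given, so 0.02 to 0.10 is assumed.

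**Step 1: redundancy.** With subject variance σ², an all-ones matrix *J* and within-subject matrix *R*, the marginal covariance is *V* = σ²*J* + *R*. For any constant *c*, *V* = (σ² − *c*)*J* + (*R* + *cJ*). If *R* is unstructured, *R* + *cJ* is also unstructured, so the data cannot separate the two parts. An unstructured *R* has *k*(*k*+1)/2 parameters. Adding σ² gives one more, but the rank of the map to *V* does not rise:

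| *k* | parameters with subject effect | rank |
|---|---|---|
| 3 | 6 + 1 = 7 | 6 |
| 5 | 15 + 1 = 16 | 15 |
| 12 | 78 + 1 = 79 | 78 |

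The shortfall is one at every *k* checked (3, 4, 5, 6, 8 and 12). If the subject effect is kept during the fallback, then at *k* = 5 Toeplitz has 6 parameters and rank 5, compound symmetry 3 and rank 2, and AR(1) 3 and rank 3. AR(1) is then the only listed structure without the redundancy.

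**Step 2: what remains estimable.** *V* is the same for every split between σ² and *R*. The fixed effects, including the treatment differences, depend on the covariance only through *V*. They are unaffected.

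**Step 3: fallback order.** Parameters without the subject effect are *k*(*k*+1)/2 for unstructured, *k* for Toeplitz, 2 for AR(1) and 2 for compound symmetry. At *k* = 5 the stated order is 15 → 2 → 5 → 2. AR(1) is the special case of Toeplitz in which the covariances decline geometrically with lag. The sequence therefore drops to a special case and returns to the structure containing it only if the special case fails. Without the subject effect every structure has full rank at *k* = 5 (15/15, 5/5, 2/2, 2/2), and the descending order is 15 → 5 → 2.

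**Step 4: strata.** If the strata explain *R*² of the remaining variance, the standard error without them relative to that with them is 1/√(1 − *R*²):
- *R*² = 0.02: 1/√0.98 = 1.01
- *R*² = 0.05: 1/√0.95 = 1.03
- *R*² = 0.10: 1/√0.90 = 1.05

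Adding both factors costs (3 − 1) + (3 − 1) = 4 fixed-effect degrees of freedom, against 300 planned subjects (Section 2.3.4).

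**The case against.** The strongest replies, and what stands of each:

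- **Section 4.4 is not flatly contradicted.** A reader might infer that the WPS model breaks a general rule. But Section 4.4 defers to Section 8, where the WPS model is specified, and Section 4.1 makes covariate adjustment optional and leaves it to each analysis. This stands. What remains is an unexplained departure from the reason given in Section 4.4, which applies equally to WPS, and from the other models in Section 8.3.
- **The model can be fitted.** A reader might infer that it is not identifiable and yields no valid treatment comparison. Step 2 shows otherwise: only the split between subject variance and the unstructured matrix is undetermined. The phrase may also just name the subject as the repeated-measures unit. In that case the point is a wording clarification and the false trigger disappears.
- **The effect of omitting the strata is assumed and conservative.** This stands. No figure in the SAP supports 2% to 10%, baseline is already in the model, and the error is towards wider intervals.
- **The fallback harm is conditional.** It needs the unstructured fit to fail, then AR(1) to converge and be materially wrong. None of this has been shown. The sequence is also fully prespecified, so it leaves no room for selective choice.
- **Changing the model is not free.** Section 4.3 has all double-blind outputs produced at the Week 52 lock, when treatment codes are released to the reporting team. Sections 2.2.1.3 and 8.1.1 refer to outputs already produced. Section 8.4 lists no WPS analysis at Week 156. Replacing the model now would alter a prespecified analysis after unblinding. This stands and limits the remedy.

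**Conclusion.** The point holds as a minor specification fault. The WPS model omits both stratification factors, out of line with the other models in Section 8.3. Its fallback order accepts a restrictive AR(1) without trying the Toeplitz structure that contains it. Taken literally, its covariance is redundant by one parameter, which can start that fallback needlessly.

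The size is small. Standard errors are about 1% to 5% too wide if the strata explain 2% to 10% of the variance remaining after baseline. That range is an assumption. The omission does not bias the treatment difference. The one-parameter redundancy does not depend on the number of visits, but it does depend on reading the subject effect as a separate random term. The effect of accepting AR(1) cannot be sized from the document.

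Severity is the lowest: p-values are nominal, WPS is outside the testing hierarchy, and no primary or secondary conclusion is touched.

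**What to change.** Revise the one paragraph on WPS in Section 8.3:

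1. Add region and MRI/CRP classification as fixed effects. Use the classification recalculated from source data (Section 4.8), as in the other models.
2. Specify the covariance only through the within-subject repeated structure, with no separate random subject effect. If subject was only meant as the repeated-measures unit, say so.
3. Order the fallbacks unstructured, Toeplitz, then a two-parameter structure. AR(1) and compound symmetry have two parameters each and neither contains the other, so their relative order is a choice, but it should be fixed in advance.

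The cost is 4 degrees of freedom per model, a short text change and a rerun of eight models, with no new data. Because the double-blind outputs already exist, keep the prespecified analysis and report the revised model beside it as a labelled supplementary analysis. State which covariance structure each question actually used.

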### 8.3.1 Derivation of other efficacy variables

Derivations of other efficacy variables not covered in the primary or secondary variables are provided below.

#### 8.3.1.1 Bath Ankylosing Spondylitis Metrology Index (BASMI)

The BASMI characterizes the spinal mobility of a subject with AS and consists of 5 clinical measures to reflect axial status: CCI

Each of the 5 movements is scored according the linear BASMI definition (see table below). The mean of the 5 scores provides the BASMI score. The higher the BASMI score the more severe the subject’s limitation of movement due to their AxSpA.

##### BASMI linear definition

$S = (21.1 \text{ cm} - A) / 2.1 \text{ cm}$	CCI
$S = (A - 8 \text{ cm}) / 3 \text{ cm}$	
$S = (7.4 \text{ cm} - A) / 0.7 \text{ cm}$	
$S = (124.5 \text{ cm} - A) / 10 \text{ cm}$	
$S = (89.3^\circ - A) / 8.5^\circ$	
Always with the additional condition $0 \leq S \leq 10$	

S = score, A = assessment

For CCI, take the mean of the left and right measurements, if both are available. Otherwise, the available measurement will be used.

For the CCI, values greater than 9.0 cm (Maksymowych 2006) will be flagged as invalid and treated as if they were missing values. The below imputation rules apply for BASMI.

If 1 or 2 clinical measures for the BASMI are missing at one visit, the missing measure will be imputed by carrying the last observation forward, and the BASMI will be calculated accordingly. If more than 2 items are missing, the BASMI score will be treated as missing.

### **8.3.1.2 Total spinal pain**

Total spinal pain will be recorded based on a NRS ranging from 0 to 10, where 0 represents no pain and 10 represents most severe pain.

### **8.3.1.3 SI joint radiographs**

SI joint radiographs will be read by two reviewers, with adjudication (if applicable), to assess for the presence and severity of sacroiliitis according to mNY criteria for AS in the right and left SI joint separately.

A grading from 0 to 4 will be assigned corresponding to 0 = Normal, 1 = Suspicious but not definite, 2 = Minimal: some sclerosis, minimal erosion, no marked joint space narrowing, 3 = Moderate: definite sclerosis, both sides of the joint with erosions and/or joint space change, and 4 = Ankylosis: complete obliteration of the SI joint with or without sclerosis. Readers will also classify the subjects as mNY-negative or mNY-positive.

A mean grading will be calculated per subject and visit using the four SI grading results (the left and right joint grades read by the 2 readers). If a third adjudication reading is required, then all 6 grades will be used to calculate the mean grade per visit.

If there is disagreement between the 2 readers in the classification of the subject (mNY-negative or mNY-positive), then the 3rd readers adjudication classification will be used for analysis.

Subjects who are positive at baseline (and hence should not have been enrolled) will be excluded from the categorical endpoint analysis of subjects who change from mNY-negative to mNY-positive during the study.

### **8.3.1.4 Tender and Swollen Joint Counts (44 joints evaluation)**

Tender joint counts (TJC) and swollen joint counts (SJC) will be carried out on the following 44 joints:

- Upper body (4) – bilateral sternoclavicular and acromioclavicular joints
- Upper extremity (26) – bilateral shoulders, elbows, wrists (includes radiocarpal, carpal and carpometacarpal bones considered as a single unit), metacarpophalangeals (MCPs) I, II, III, IV, and V, and thumb interphalangeals (IPs), and proximal IPs (PIPs) II, III, IV, and V
- Lower extremity (14) – bilateral knees, ankles, and metatarsophalangeals (I, II, III, IV, and V)

The assessment for swelling and tenderness is made on 44 joints from the above list. Artificial, ankylosed, and missing joints are excluded from swelling and tenderness assessments.

Each joint is scored for tenderness as follows:

0 = None (not tender)

1 = Positive (tender)

Each joint is scored for swelling as follows:

0 = None

1 = Detectable

TJC and SJC are calculated as the sum of tender and swollen joints, respectively, among the 44 joints. Both TJC and SJC range from 0 to 44.

If there are missing observations for tender or swollen joints then the remaining observations will be assessed and weighted by dividing by number of non-missing and then multiplying by 44 for the joint count. If a joint is not evaluable at Baseline, then that joint is set to missing throughout the study.

If data for more than 50% of the joints are missing at the time of a given assessment, then no imputation will be done and the total TJC or SJC will be set to missing for that visit.

TJC summaries will be based only on those subjects with at least one tender joint at Baseline. Similarly, SJC tables will be based only on those subjects with at least one swollen joint at Baseline.

### 8.3.1.5 Patient's Global Assessment of Disease Activity (PGADA)

PGADA will be recorded based on an NRS describing how active the subject's spondylitis was on average over the past week. The range of the scale is from 0 to 10, where 0 represents not active and 10 represents very active.

### 8.3.1.6 Physician's Global Assessment of Disease Activity (PhGADA)

PhGADA is recorded by the physician on a VAS ranging from 0 to 100, where 0 is "very good, asymptomatic and no limitation of normal activities" and 100 is "very poor, very severe symptoms which are intolerable and inability to carry out all normal activities."

### 8.3.1.7 C-reactive protein (CRP)

For CRP values below the lower limit of quantification (<4mg/L), half the lower limit (2mg/L) will be used as the imputed value.

### 8.3.1.8 Spinal mobility

The following spinal mobility assessments will be performed in addition to those performed for the BASMI:

- Occiput to wall distance
- Chest expansion

### 8.3.1.9 Enthesitis (MASES)

The MASES comprises 13 items

CCI [REDACTED]

[REDACTED] (Heuft-Dorenbosch et al, 2003) each scored as 0 = yes or 1 = no and then summed for a possible score of 0 to 13, with higher scores indicating worse enthesitis.

If 7 or more items are available, MASES will be imputed by dividing the sum score with the number of assessments and multiplying the result with 13. If less than 7 times are available, MASES will be treated as missing.

Summaries of MASES will be restricted to the subset of subjects with enthesitis present at Baseline. Presence of enthesitis at Baseline will be defined as a Baseline MASES score >0.

#### **8.3.1.10 Short-Form 36-item Health Survey (SF-36)**

The SF-36 (Version 2, standard recall) is a 36 item generic HRQoL instrument that uses a recall period of 4 weeks. Items are grouped into 8 domains as follows: Physical Functioning (10 items), Role Physical (4 items), Bodily Pain (2 items), General Health (5 items), Vitality (4 items), Social Functioning (2 items), Role Emotional (3 items), Mental Health (5 items), and a further unscaled single item (Q2) for perceived stability or change in health (Health Transition) during the last year. The concepts represented by these domains contribute to physical, mental, and social aspects of HRQoL.

The SF-36 domains (subscores) are scored so that a higher score indicates a better health state.

QualityMetric Health Outcomes™ Scoring Software will be used to calculate norm-based scores for the following domains:

- Physical Functioning (PF)
- Role Physical (RP)
- Bodily pain (BP)
- General health (GH)
- Vitality (VT)
- Social Functioning (SF)
- Role Emotional (RE)
- Mental health (MH)
- Mental Component Summary (MCS)
- Physical Component Summary (PCS)

#### **8.3.1.11 ASAS-NSAID score**

The ASAS-NSAID score is a tool that has been developed to measure the magnitude of NSAID intake during clinical studies (Dougados et al, 2011). Using the concomitant medication NSAID data, the start and stop dates of each medication will be compared to study intervals to determine the dosage and frequency that each NSAID was being taken during the study. Intervals will be weekly from Week 0 to Week 2, bi-weekly up to Week 4 and then every 4 weeks until Week 52.

Subjects not taking NSAIDs in an interval will have an ASAS-NSAID score of 0.

The general formula for calculating the ASAS-NSAID score in an interval is as follows:

- $(\text{equivalent NSAID score}) \times (\text{days of intake during period of interest}) \times (\text{days per week}) / (\text{period of interest in days})$

Each of the components of the above calculation are described below:

- Equivalent NSAID score: This is reported in terms of NSAID equivalent dose in mg/day on a 0–100 scale where the 150mg equivalent diclofenac is set to 100. An NSAID equivalence

table was developed based on a survey of ASAS members. The table including the consensus equivalence score for various NSAIDs can be found in Appendix 13.3.

- Days of intake during period of interest: Equivalent to the total number of days covered during the period that is being measured.
- Days per week: Proportion of days per week when the NSAID is taken. This is collected in the categories described in the days with intake category listed above. Each category corresponds to a score as follows (score in parentheses):
  - Every day or QD (7/7)
  - $\geq 5$  days/week (6/7)
  - 3-5 days/week (4/7)
  - 1-3 days/week (2/7)
  - $< 1$  day/week (0.5/7)
  - No NSAID intake (0)
- Period of interest in days: Refers to the number of days covered for a given NSAID. If only 1 NSAID was taken during the entire period of interest, this will be the same as days of intake during period of interest.

Dougados, et al provide the following example. If during a period of interest (between two visits) of 6 months, the subject has taken piroxicam 20mg during 4 months and if during this 4-month period he has taken piroxicam 3–5 days per week the calculation is as follows:

- $100$  (20mg piroxicam score)  $\times 120$  (4 months)  $\times 4/7$  (3–5 days/week)/ $180$  (6 months) = 38.1

If the subject has used 10mg piroxicam during the remaining 2 months on 2 days a week, the NSAID score for this period is:

- $50$  (10 mg piroxicam score)  $\times 60$  (2 months)  $\times 2/7$  (1–3 days/week)/ $180$  (6 months) = 4.8

In this example the total score for the 6 month period is 42.9 (38.1 plus 4.8).

For the observed case analysis, only intervals that end on or prior to end of the double-blind treatment period will be included. For the LOCF analysis, all data will be included for all intervals up to Week 52 (1 year) irrespective of whether the subject is on double-blind or open-label study medication.

